## **STATISTICAL CONSIDERATIONS**

### 3.f. Statistical Analyses

Outcome measures will be collected at baseline and weekly for the 8 weeks of participation. Repeated measures models will be used to assess the changes over time in suicidal ideation and intensity of nightmares

and disturbing dreams. These models will be used to obtain estimates of the treatment effects (the changes in the outcome measure from baseline to end of randomization), estimates of the variability of the outcome measures at each time adjusted for baseline measures, and estimates of the within patient correlations over time. These estimates will be used in the design of a subsequent adequately-powered randomized clinical trial. Regression diagnostics, residual plots, and exploratory analyses will be done to find appropriate transformations to satisfy the 1) linearity, 2) homogeneity of variances, and 3) normality assumptions. While we assume compound symmetry for the correlation among repeated measures, we will also consider other covariance patterns. We will also assess the correlation amongst all the measures collected over time. While our sample size is small, we will also use a mediation analysis to determine the degree to which nightmares are responsible for (or mediate) the changes in suicidal ideation.{Baron, 1986 1126 /id}{MacKinnon, 2004 1260 /id;Efron, 1979 1261 /id}

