## Project Summary

Numerous (>40) epidemiologic reports have linked insomnia and nightmares to suicidal ideation and suicide death. We are presently engaged in a project which tests the hypothesis that treatment of insomnia in depressed patients with hypnotic medications will reduce the intensity of suicidal ideation. This ongoing project is called Reducing Suicidal Ideation Through Insomnia Treatment (REST-IT).

We have now acquired and analyzed new data since the inception of the present project that reveals that nightmares and disturbing dreams are more strongly related to the intensity of suicidal ideation than is insomnia itself. We therefore propose to target treatment of nightmares in suicidal patients experiencing nightmares as part of post-traumatic stress disorder (PTSD). This new effort is named Reducing Suicidal Ideation Through Treatment of Nightmares in PTSD (REST-ON-PTSD). REST-ON-PTSD will offer treatment with open label selective serotonin reuptake inhibitors (SSRIs) for PTSD, or open label treatment for bipolar disorder, combined with randomization to prazosin versus placebo. SSRIs are the only medications approved by the FDA for treatment of PTSD, while prazosin is the best-practice pharmacologic treatment for nightmares.{Aurora, 2010 1365 /id} REST-ON-PTSD is designed to be a small, randomized controlled clinical trial intended to generate pilot data to estimate effect sizes for prazosin treatment in reducing suicidal ideation in suicidal PTSD outpatients who have nightmares and disturbing dreams, with the following Specific Aims:

Primary Aim: We will estimate the effect size of prazosin on the intensity of suicidal ideation in PTSD outpatients with nightmares and disturbing dreams.

Hypothesis 1. Prazosin, combined with an SSRI or open label treatment for bipolar disorder, will reduce suicidal ideation in suicidal PTSD outpatients who have nightmares and disturbing dreams.

Secondary Aim: We will estimate the effect size of prazosin in reducing the intensity of nightmares and disturbing dreams in suicidal PTSD outpatients with nightmares and disturbing dreams.

Hypothesis 2. Prazosin, combined with a SSRI or open label treatment for bipolar disorder, will reduce the intensity of nightmares and disturbing dreams in suicidal PTSD outpatients with nightmares and disturbing dreams

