Participants were 18-70 years old, with either (a) sleep latency  $> 30$  minutes and sleep efficiency  $< 85\%$  at least 4 nights per week. {Edinger, 2004 553 /id} All participants met a DSM-IV diagnosis of unipolar MDE per Structured Clinical Interview for DSM-IV (SCID), {American Psychiatric Association, 1994 286 /id} and a HRSD24 score  $\geq 20$ . {Hamilton, 1960 371 /id} All participants completed one night of baseline polysomnogram (PSG) which showed no clinically significant sleep apnea (Apnea/Hypopneas index  $>15$ ) or Periodic Limb Movement Disorder (PLM arousal index  $>15$ ), following standard measurement procedures described elsewhere. {McCall, 2009 1052 /id}

The average age of the randomized sample was  $41.5 \pm 12.5$  years, and 66% were women, with 23.2% minorities. At baseline, the average HRSD24 score was  $27.1 \pm 3.9$ , and the average ISI score was  $20.7 \pm 4.0$ . Scale for Suicide Ideation (SSI) scores were analyzed using generalized linear mixed models for repeated measures with predictor variables being insomnia (ISI scores), the mood item, and the anhedonia item from the HRSD24. Baseline SSI was  $3.7 \pm 5.2$ , with 55% having a SSI score  $\geq 1$ , and 37% of patients having a SSI score  $\geq 3$ .

The model with ISI as the predictor for SSI was significant with the regression coefficient corresponding to ISI being positive ( $\beta=0.055$ , SE=0.02,  $p<0.01$ ). Other univariate models found that the depressed mood item was also a significant predictor of suicidal ideation ( $p<0.005$ ), but anhedonia was not a predictor of suicidal ideation ( $p=0.9$ ). A multivariate model simultaneously including both the insomnia and the depressed mood items found that both were independent predictors of suicidal ideation (both  $p<0.05$ ). Our findings confirm that the intensity of insomnia predicts intensity of suicidal ideas during a clinical trial of MDE, even after adjusting for depressed mood and anhedonia. {McCall, 2010 1193 /id}

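### Section 3.f names baseline adjustment for the variability but not for the treatment effect, so the effect may be an unadjusted change score that does not match the SD carried into the next trial

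*Combined protocol and SAP*

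**What the plan says.** The Project Summary sets the primary aim: "We will estimate the effect size of prazosin on the intensity of suicidal ideation in PTSD outpatients with nightmares and disturbing dreams". Section 3.f (Statistical Analyses) is the whole analysis plan. It states that "Repeated measures models will be used to assess the changes over time in suicidal ideation and intensity of nightmares"; bad dreams are covered in the same sentence. The fitted models are to supply three things:

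- for the effect, "estimates of the treatment effects (the changes in the outcome measure from baseline to end of randomization");
- for the spread, "estimates of the variability of the outcome measures at each time adjusted for baseline measures";
- for the correlation, "estimates of the within patient correlations over time".

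On covariance it says: "While we assume compound symmetry for the correlation among repeated measures, we will also consider other covariance patterns". On use it says: "These estimates will be used in the design of a subsequent adequately-powered randomized clinical trial".

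Four things are not stated: whether the effect is baseline-adjusted, whether baseline enters as a covariate or as one of the repeated responses, which SD will standardize the effect, and that the change is contrasted between prazosin and placebo.

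**The concern.** The pilot exists to deliver an effect size and a variance for planning. An unadjusted change from baseline has one variance and a baseline-adjusted outcome has another, usually smaller. An analyst who follows 3.f literally could take the effect from a model with baseline among the responses and the SD from a model that adjusts for baseline.

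Two things are then at stake. In the pilot, the primary estimate is less precise than the collected data allow, and it carries more of any chance baseline imbalance between two arms of 10. In the next trial, dividing a change-score effect by a baseline-adjusted SD gives a standardized effect that is too large for a change-score analysis.

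**Working it through.** **Inputs.** The plan gives no alpha, power, target difference or sample-size formula, so there is no stated figure to reproduce.

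- Arm size n = 10: 20 participants randomized 1:1 (3.e.2). The block count under randomization in 3.e.4, 5 × 2 = 10, does not reach 20 and is not used.
- SSI SD: 5.2 (3.e.1, baseline of the earlier depression and insomnia trial) or 6 (6.d, response on confidentiality limits, another outpatient group). Both are illustrations.
- Baseline-to-end correlation ρ: not given. Assumed 0.3, 0.5 and 0.7, with 0.1 and 0.9 as extremes.
- Also assumed: normal data, one baseline and one final value, no dropout and, until step 5, equal SDs at baseline and end. Step 4 adds two-sided alpha 0.05, 80% power and a 3-point SSI difference.

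**1. What a literal fit estimates.** Put baseline among the responses with categorical time and free arm-by-time means. With complete data, the between-arm contrast in change is exactly the difference in mean raw change. Nothing in that fit adjusts for baseline.

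**2. The two variances.**

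- Unadjusted change: 2(1 − ρ)SD².
- Baseline-adjusted: (1 − ρ²)SD².
- Ratio, adjusted to change: (1 + ρ)/2 = 0.65, 0.75, 0.85.

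**3. The pilot.** The slope must be estimated. With 18 within-arm degrees of freedom this multiplies the adjusted variance by 1 + 1/16 = 17/16.

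| ρ | (1 + ρ)/2 × 17/16 | Cut in variance | Simulated SDs of the effect, change and adjusted (SD 5.2) | Squared ratio |
|---|---|---|---|---|
| 0.3 | 0.69 | 31% | 2.747, 2.276 | 0.69 |
| 0.5 | 0.80 | 20% | 2.321, 2.078 | 0.80 |
| 0.7 | 0.90 | 10% | 1.798, 1.704 | 0.90 |

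The simulation used 40,000 trials. Both estimators centred on the true difference of −3 (−3.005 and −3.011 at ρ = 0.5), so the issue is precision and not bias. The SE of the baseline arm difference is SD × √(2/10): 2.3 SSI points at SD 5.2 and 2.7 at SD 6. Within a single pilot the two estimates differ with an SD of 1.7, 1.3 and 0.8 SSI points at ρ = 0.3, 0.5 and 0.7 (SD 5.2).

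**4. The next trial, if sized with the adjusted SD but analysed on unadjusted change.**

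- The standardized effect is inflated by √(2/(1 + ρ)) = 1.24, 1.15, 1.08.
- N falls short by 1 − (1 + ρ)/2 = 35%, 25%, 15%.
- Power is Φ(√((1 + ρ)/2) × 2.802 − 1.960) = 62%, 68%, 73% instead of 80%.
- Illustration (SD 5.2, ρ = 0.5, 3 points): the SDs are 5.20 for change and 4.50 adjusted, requiring 48 and 36 per arm. Analysing 36 per arm on change gives 69% after rounding N up.
- Extremes: 85 against 47 per arm at ρ = 0.1 (power 55%), and 10 against 9 at ρ = 0.9 (power 78%).

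**5. Unequal variances.** Let k = SD at baseline / SD at end. The variance ratio, change to adjusted, is (k² + 1 − 2ρk)/(1 − ρ²) = 1 + (k − ρ)²/(1 − ρ²). At ρ = 0.5 this is 1.05 for k = 0.7, 1.33 for k = 1 and 1.85 for k = 1.3. When k = ρ, change loses nothing, and with 10 per arm adjustment would cost the 1/16 from step 3.

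**The case against.** A reader might infer that 3.f does mix two scales, that precision is lost, and that the next trial will be underpowered. The documents do not support that.

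- One set of models is said to give all three estimates. The parenthesis names a quantity, not an estimator, and the reference to baseline-adjusted variability shows that adjustment was contemplated.
- Both quantities are in SSI points, and under randomization both contrasts have the same expectation. With baseline as a covariate, the arm effect on change equals the arm effect on the final value exactly. A change from baseline paired with a baseline-adjusted SD is then coherent.
- No document describes the next trial's analysis. If it adjusts for baseline, the adjusted SD is the right one and the shortfall disappears.
- The SDs are borrowed. In the sample behind 5.2, the description reads "with 55% having a SSI score" of at least 1 and only 37% reached 3. This trial requires at least 3 (3.e.3), which truncates baseline and makes equal variances doubtful.
- The pilot SD is itself loose. On 18 degrees of freedom its 95% interval runs from 0.76 to 1.48 times the estimate, so the implied N runs from 0.57 to 2.2 times.
- The plan already provides for within-patient correlations, which go most of the way towards converting between scales.

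All of this stands, and it makes the sizes conditional. It does not close the gap: the change-score fit is a natural reading of 3.f, and noise in the SD is no reason to add an avoidable mismatch.

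**Conclusion.** The point holds as a conditional one. Section 3.f leaves open whether the effect is baseline-adjusted while saying that the variability is. If baseline is a covariate, or baseline means are constrained equal across arms, there is no mismatch and no avoidable loss.

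If baseline is a free response, the pilot forgoes a variance reduction of about 31%, 20% or 10% (ρ = 0.3, 0.5, 0.7; 10 per arm; equal variances), and the effect does not belong with the adjusted SD. The 35%, 25% or 15% shortfall needs one condition more, that the next trial is analysed on unadjusted change. At ρ = 0.9 little is left: the variance ratio is 2/1.9 = 1.05.

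This should be changed because the effect size is the primary deliverable and the remedy uses data already planned. It does not invalidate the pilot.

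**What to change.** Rewrite the estimation sentence in 3.f to say the following.

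1. The treatment effect is the prazosin-minus-placebo difference in SSI, and separately in DDNSI, at the end of randomized treatment. It comes from one longitudinal model with categorical week and arm-by-week terms that adjusts for baseline, either as a covariate or by constraining baseline means to be equal across arms. In the constrained form, let the baseline variance differ from the later ones, since plain compound symmetry forces them equal.
2. The planning SD comes from that same model. Report with it the raw SDs at baseline and end and the baseline-to-end correlation, so that the next trial can convert between scales.
3. The planning SD applies to a baseline-adjusted analysis of the next trial.

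One reconciliation comes first. Section 3.e.5 lists SSI at baseline, weeks 1, 2 and 4, and by telephone a month after treatment, while 3.f and 6.g describe weekly collection. The sections must agree so that an SSI at the end of randomized treatment exists.

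The cost is a few sentences and a few degrees of freedom: one for the baseline slope in the covariate form, plus the week and arm-by-week terms. If weekly collection stands, no new data are needed.

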### 3.g. Potential Pitfalls and Alternative Solutions

- Alternatives to Prazosin: Clonidine has been reported to have some effect in reducing nightmares but is generally described as less effective than prazosin. In contrast, prazosin is the best-practice pharmacologic treatment for nightmares is prazosin.{Aurora, 2010 1365 /id} Some psychotherapies that hold promise for the treatment of nightmares, notably imagery rehearsal therapy.{Hansen, 2013 1370 /id} However, this approach is unlikely to be adopted by most physicians managing PTSD. This approach may well prove to be useful but deserves its own separate line of inquiry.

### Conclusions and Future Directions

Results from this project will provide a first clue as to whether a SSRI-prazosin combination treatment is a candidate treatment for reducing the intensity of suicidal ideation in PTSD patients. If so, it opens the possibility that other forms of nightmare treatment (i.e., imagery rehearsal therapy) may also have benefit. This project will also provide support for hypothetical mechanisms explaining the association between nightmares and suicidal ideation.

## 6. PROTECTION OF HUMAN SUBJECTS

### 6.a Subject selection procedures

The subject selection features of REST-ON-PTSD are intended to: (1) yield a sample with PTSD associated with suicidality, and (2) exclude patients who might be harmed by exposure to psychotropics, including pregnant women. Three procedures are used to assure participant safety at the baseline assessment: the Mini Mental State Exam (MMSE),{Folstein, 1975 78 /id} a pregnancy test for women of conception age, and a baseline Columbia- Suicide Severity Rating Scale (C-SSRS) score.

A MMSE score < 24 is statistically abnormal at any age and is consistent with global cognitive deficits such as seen in dementia.{Crum, 1993 313 /id}

All women of child bearing age will complete a urine pregnancy test at the first face to face visit. Persons excluded because of overly intense suicidal ideation (C-SSRS suicidal ideation score >3) will be evaluated for safety and perhaps the need for psychiatric hospitalization.

The additional subject exclusion factors are:

- History of sensitivity or allergy to prazosin or quinazolines
- History of fainting or syncopal episodes in the last 6 months
- History of hypotension
- Automatic Blood Pressure readings with systolic BP <90, or diastolic <50, either sitting or standing.
- Planned use of sildenafil, tadalafil, or similar erectile dysfunction medication

### 6.b. Recruitment and Consent Procedures

#### 6.b.1. Recruitment

**6.b.2. Consent procedures** The Project Manager will describe the overall study design, and will detail the time commitment required from the participant. The project manager provides a copy of the consent form, allowing enough time for the participant to read the consent form and ask questions, and sign the consent form. We will assure the capacity of each patient to understand the risks and benefits of participation by assessing each participant with the Evaluation to Sign Consent (ESC). The ESC was developed by Love in 1988 (unpublished; as cited in Deronzo, Conley, & Love, 1998).{Deronzo, 1998 1446 /id} The ESC assesses the factual understanding of subjects, is composed of five items, and can be adapted to any research design.

### 6.c. Potential risks

The risks of participating in this project are related to prazosin. The primary risk from prazosin is orthostatic hypotension. Prazosin is an  $\alpha_1$  adrenergic receptor blocker approved for use as an antihypertensive. The cardiovascular effects of the drug were fully characterized more than 30 years ago.{Colucci, 1982 1369 /id} It generally has no effect on heart rate. The most common side effects at these doses in hypertensive patients are: dizziness 10.3%, headache 7.8%, drowsiness 7.6%, lack of energy 6.9%, weakness 6.5%, palpitations 5.3%, and nausea 4.9%. The most common side effects (>5%) when given to patients with PTSD are: lightheadedness 25%, nasal congestion 22%, and palpitations (6%).{Raskind, 2013 1474 /id} We will manage the risk of hypotension by excluding participants with a history of fainting or syncopal episodes in the last 6 months, history of hypotension, or automatic Blood Pressure readings with systolic BP <90, or diastolic <50, either sitting or standing. The risk of side effects might be severe if the patient took an intentional overdose,

although limited reports of overdose suggest a low acute toxicity.{Lip, 1995 1447 /id}

#### **6.d. Safeguards**

The Star\*D trial was among the first NIH-sponsored trials to follow the 2001 NIH guidelines for studies which included patients at risk of suicide. <http://www.nimh.nih.gov/health/topics/suicide-prevention/issues-to-consider-in-intervention-research-with-persons-at-high-risk-for-suicidality.shtml> {Nierenberg, 2004 924 /id} The guidelines have several stipulations, and we have responded accordingly:

- 1) "Provide specific inclusion criteria and their measurement with regards to suicidality"

Response: Patients included in the study will have a Scale for Suicidal Ideation (SSI) scores  $\geq 3$  but with C-SSRS suicidal ideation scores of  $\leq 3$ . This range defines patients with mild and moderate suicidal ideation, but with no intent to commit suicide. This inclusion range for suicidal ideation is consistent with prior clinical trials of suicidal patients. {Brown, 2005 1468 /id; Grunebaum, 2012 1470 /id}

"Specify the criteria for withdrawal from the treatment trial with regard to increased suicidality, increased related symptoms, lack of treatment response, and treatment side effects, and what alternative treatment or referral will be offered."

Response: The decision to withdraw the participant from research treatment will be based upon either the participant's view or the research psychiatrist's opinion that the patient is experiencing severe suffering, is at imminent risk for suicide, or is functionally decompensating. The clinician's opinion will be informed on the basis of the DDNSI, the PCL-S, and the C-SSRS, but the decision to withdraw a participant will be based upon a combination of psychometrics along with global clinical judgment. If a participant is withdrawn from the study, then he or she will be offered care-as-usual, or hospitalization if necessary.

- 2) "Consider and establish criteria for hospitalization, where the hospitalization will take place, and the procedures within the hospital that provide additional safety"

Response: Hospitalization will be offered if the patient is judged at imminent risk of suicide, is functionally decompensated, or needs specialized treatment outside of the protocol (such as ECT), according to the global clinical judgment of the study psychiatrist. Hospitalization would take place in the inpatient units of Georgia Regents Medical Center, or East Central Regional Hospital, or similar regional facility.

- 3) "Describe procedures in the protocol for managing increases in suicidality, and how research staff is trained and available to provide clinical management"

Response: Managing increases in suicidality is predicated upon detection of such increases. Although we proposed to examine participants weekly, we recognize that suicidal ideation may emerge suddenly and unpredictably. Therefore, research staff will make at least one mid-week phone call to each participant for the first 2 weeks to check on their well-being and assure them that the study staff is available. At each scheduled study visit, the protocol will quantify suicidality 2 ways. First, the participant will complete the

Scale for Suicide Ideation. This information flows from the research staff to study psychiatrists at the time of the visit. Second, the research psychiatrist will administer the Columbia Suicide Severity Rating Scale (C-SSRS), allowing for a thorough review for the presence of any self-injurious behavior since the last visit or the development of any preparatory suicidal planning, as categorized by the C-SSRS.{Oquendo, 2003 1195 /id} Patients judged by the study psychiatrist to be at increased risk of suicide will have an increased frequency of research visits, have smaller supplies of research medication, or may be withdrawn from the study and possibly hospitalized.

- 4) "Have a procedure for emergency coverage that is clearly understood by the clinical research staff, study participants, and families"

**Response:** At the time of consent, participants will receive clear instructions for how to reach study staff during the daytime, and how to access after-hours coverage as provided through each site. Psychiatry residents-in-training who receive emergency calls from participants after-hours will be instructed to call the local principal investigator immediately, regardless of the time of day. The PI or designated co-I will be continuously available to the respective on-call residents to guide crisis management and assess for the primary suicidal endpoints, if necessary by phone.

- 5) "As part of the consent process, consider having explicit discussion with relevant family members, guardians, or friends that includes the risks inherent when study participants are suicidal (risk of death, side effects of treatment)"

**Response:** Involvement of the participant's family will be encouraged, starting by asking potential participants to bring their families to the first face-to-face screening visit.

- 6) "Consider and identify the limits of confidentiality with respect to suicidality, as well as other circumstances"

**Response:** When a participant has emergent suicidality defined as an increase of 6-points (one standard deviation of SSI scores in [name] outpatients), we will inform the participant of our intent to share this with the relevant family, and the consent form will reflect this.

- 7) "Consider the impact of suicidality on the study participant's capacity to give informed consent"

**Response:** Consent will be obtained only from persons who normally would not meet criteria for emergent psychiatric hospitalization, i.e., C-SSRS suicidal ideation score < 4.

- 8) "Determine whether additional safeguards are needed to ensure the safety of the study participants"

**Response:** No additional safeguards needed

- 9) "Consider situations in which a trial would be terminated prematurely"

**Response:** As this is a pilot study with only 20 participants, we have no statistical endpoints for early termination of the study. However, the trial would be terminated prematurely only if the Medical Monitor determined that there was a systematic increase in risk, according to the Data Safety Monitoring Plan,

below.

